- June 25, 2022: Clarified that individuals who completed Aim 1 patient focus groups would be allowed enrolled if they met criteria for the clinical trial
- June 25, 2022: Financial incentives updated to be R150 per specified study follow-up home visits (R450 for completion of all three study visits) to align with South Africa Health Products Regulatory Authority
- August 15, 2022: The trial was registered on ClinicalTrials.gov, as required by the NIH (NCT05492955).
- November 13, 2022: The trial was registered in the South African National Clinical Trial Registry, as required by the National Department of Health (DOH-27-112022-4895).

Intra- and post-trial protocol changes

- January 18, 2023: At the request of the funder, the protocol was updated to add a data safety and monitoring board (DSMB) to the previously planned data safety and monitoring plan, to conduct an independent safety review after 50% of enrollment was complete.
- January 18, 2023: The term community health worker (CHW) was replaced with community blood pressure monitor (CBPM) in the protocol and in the participant informed consent form for the clinical trial (Aim 2), as recommended by the local department of health.
- January 18, 2023: The participant informed consent forms were updated to reflect South African requirements around protection of personal information (South African POPI Act).
- May 29, 2024: After consultation with the Department of Health, a prolonged extension stage was offered to participants in the intervention arms after the 12-month study completion visit. This allowed them to consent to continue in the hypertension control program until study completion in June 2025. Individuals who declined continuation were referred back to primary care clinics for routine care.

[figure not shown]
Statistical Analysis Plan

Implementation Evaluation of a Combination Intervention for Sustainable Blood Pressure Control in Rural KwaZulu-Natal, South Africa

ClinicalTrials.gov registration Number: NCT05492955

Version: 1.0

Date: 20 October 2023

Written by:		Role:	Date:
Name	[name]	Trial statistician	
Signature			23 October 2023
Authorised by:			
Name	[name]	Head, Data Science Unit	
Signature			
Name	[name]	Co-PI	23 October 2023
Signature			
Name	[name]	Co-PI	24 October 2023
Signature			

1. Overview of trial design & aims

IMPACT-BP is a randomised controlled trial to evaluate the effectiveness of community-based, technology-supported interventions to reduce systolic blood pressure (SBP) and improve blood pressure control among individuals with uncontrolled hypertension in rural KwaZulu-Natal. The study aims to identify the optimal strategy for blood pressure management in rural South Africa.

The study will compare three treatment strategies: 1) standard of care (SOC), clinic-based management of hypertension, 2) a community blood pressure monitor-based model, in which individuals receive blood pressure cuffs, and are remotely monitored by nurses via community blood pressure monitors (CBPM) and a mobile health-based clinical decision support tool, and 3) an enhanced community blood pressure monitor-based model that includes home-based blood pressure cuffs that transmit readings over cellular networks directly to clinic-based nurses (eCBPM+). In both intervention groups, CBPMs will visit participants to record (CBMP) or verify (eCBPM+) blood pressure readings, dispense medications, and relay instructions from clinic nurses.

2. Study endpoints

The trial aims will be evaluated through the primary and secondary outcomes below, as defined in the study protocol.

Primary outcome

- Difference between arms in change from baseline in systolic blood pressure 6 months after enrolment.

Secondary outcome

- Proportion of participants with blood pressure control at 6 after enrolment (defined as systolic blood pressure <140 mmHg and diastolic blood pressure <90 mmHg)

Safety measures

- Number of adverse drug reactions.
- Proportion of participations retained in hypertension care at 6 months.

Acceptability, fidelity, sustainability, and cost-effectiveness of the interventions will also be assessed; these objectives will be covered in a separate analysis plan.

3. Eligibility criteria

Study recruitment will occur at the Nkundusi and Madwaleni primary health care clinics (PHC) in the AHRI Health and Demographic Surveillance Site (HDSS). All adults who present to these clinics during weekdays will be screened for potential enrolment.

Individuals are eligible to enrol if they:

- Are age ≥ 18 years old
- currently reside in the catchment area of the enrolment clinics with plans to remain in the area for the next 2 years
- have elevated blood pressure (systolic blood pressure >140 mm Hg or diastolic blood pressure >90 mmHg) at screening
- have evidence of at least one previous elevated blood pressure reading in the medical chart 6 months ago or earlier, to meet criteria for hypertension in the South African Department of Health guidelines which require elevated readings on at least two occasions.

Exclusion criteria are

- pregnant women, confirmed by urine β -HCG testing on the day of screening for women aged <55 years, or breastfeeding women
- symptomatic hypertension and a blood pressure >180 mm Hg systolic or 110 mmHg diastolic
- advanced chronic kidney disease (GFR <60 ml/min/1.73m²) as determined by point-of-care creatinine testing
- individuals on three or more anti-hypertensive medications at full dose

4. Randomisation

After informed consent, individuals will be randomised in blocks of 9 to one of the three study arms using the REDCap randomization module. Randomisation will be stratified by the clinic and active use of anti-hypertensive therapy at the time of enrolment.

5. Data collection

At enrolment, participants will be asked about sociodemographic characteristics, medical history and hypertension treatment history, self-reported medication adherence, quality of life, and resource allocation data to enable cost effectiveness analyses.

All participants will be followed up at 6 and 12 months after enrolment, where blood pressure will be measured by study nurses using a standardised Omron BP cuff. Blood pressure will be measured after the participant has been seated for 5 minutes. Three measurements will be taken on the same arm in the seated position, with each measurement taken 5 minutes apart. Data will also be collected on medication regimen changes and adherence, medical history including complications, hospitalizations and treatment side effects, and resource allocation, to enable estimates of program sustainability and longer term costs.

For participants who cannot be reached to schedule 6 or 12 month visits, a study staff member will attempt a home visit to collect outcome data.

6. Sample size

Based on patient attendance data from the two PHCs in our study in 2020, we estimate that there are over 1000 individuals with uncontrolled hypertension and thus eligible to enrol in the trial. We anticipate mean blood pressure at baseline will be 150/95 mmHg, with a standard deviation (SD) of 19 mmHg, based on previous studies. With 774 participants enrolled (258 per arm), we will have 80% power to detect a 5 mmHg difference between arms in the change of blood pressure from baseline to 6 months, assuming 20% loss to follow-up, a correlation between baseline and follow-up measurements of 0.5, and an alpha of 2.5% to account for multiple testing with comparisons between the SOC and both intervention arms (Table 1).

This same sample size will also give us greater than 80% power to detect an increase in the proportion of participants who achieve BP control (defined by a systolic BP <140 mmHg and diastolic BP <90mm Hg) at 6 months from 30% in the SOC arm to 45% in the interventions arms, or from 40% in the SOC to 56% in the intervention, also allowing for an alpha of 2.5% to account for multiple testing.

Table 1. Differences in change from baseline that can be detected with 80% power

N enrolled per arm	Loss to follow-up	Difference that can be detected (mmHg)	Standard deviation	Correlation between observations	Power
330	20%	5.0	19.0	0.20	80%
258	20%	5.0	19.0	0.50	80%
148	20%	7.5	19.0	0.20	80%
115	20%	7.5	19.0	0.50	80%

7. Definitions and analysis populations

All analyses will be conducted using the intention-to-treat principle, where all randomised participants will be included in the analysis regardless of adherence to the intervention.

All analyses of blood pressure will use the average of the second and third measurement as the blood pressure measurement for that visit. In the primary analyses, participants who are missing any of the three measurements will be considered to be missing blood pressure data for that visit. As a sensitivity analysis, individuals with fewer than three measurements will be included, using the average if there are two, or a single measurement if only one is available.

For outcomes that are based on data collected at the 6 month visit, the primary analyses will be restricted to participants with the relevant outcome data at 6 months (complete case). For outcomes that use data collected at both the 6 month and the 12 month visits, all participants with outcome data at either visit will be included (see section 10).

Sensitivity analyses will also be conducted where those with missing blood pressure data at a particular visit will be treated as having no change in blood pressure or having uncontrolled blood pressure. The primary analysis will be based on participants with complete blood pressure information; however multiple imputation of missing outcome values may also be used for exploratory analyses (see section 10).

For all outcomes, the primary analysis will be adjusted for clinic and active use of hypertension medication (i.e. the randomisation strata covariates) and blood pressure at baseline. Further, additional analyses adjusted for covariates that are known a

priori to be associated with blood pressure (e.g. age, sex, obesity, co-morbidities), or those that show baseline imbalance, may be conducted to explore the robustness of our results.

An interim analysis may be performed after all participants have completed their 6 month visit, since the primary outcome relates to this time. Data analysis will not begin until the database has been locked and the analysis plan has been signed.

8. Description of the cohort at baseline

In order to assess the comparability of the treatment groups, baseline characteristics of participants will be summarised by arm. Continuous variables will be summarised using means and standard deviations, and categorical variables will be summarised using frequencies and percentages. No formal statistical testing will be done.

Following the CONSORT guidelines, the number of individuals screened, the number who were eligible, and the number enrolled in the trial will be illustrated in a flowchart. Reasons for non-eligibility and non-enrolment will be tabulated. The flow chart will also show the number of participants attending the follow-up visits at 6 and 12 months, and the number withdrawing from the study, by trial arm.

The baseline characteristics of participants who are included in the analyses at 6 months (primary outcome) and 12 months and those who are not included (either because they withdrew, were lost to follow-up, or missed the relevant visit) will be summarised and compared descriptively.

9. Statistical methods

The statistical methods that will be used to address each study objective are described below. To correct for multiple testing when comparing the two intervention groups with the control group (SOC), we will use the Bonferroni correction with a significance p-value of 0.025

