9.1 Primary objective

The primary objective of the trial is to examine the effect of the interventions on the change from baseline in systolic blood pressure 6 months after enrolment. The mean

and SD systolic blood pressure, and the mean and SD change from baseline, at the 6 and 12 month visits will be summarised by treatment arm.

Linear regression will be used to estimate the mean difference, and its 95% confidence interval (CI), between each intervention and SOC (i.e. CBPM vs SOC and eCBPM+ vs. SOC) in the change from baseline at 6 months. The response variable will be systolic blood pressure at 6 months; the model will include treatment arm, clinic, active use of hypertension medication and baseline systolic blood pressure.

In secondary exploratory analyses, we will adjust for baseline values of age, sex, body mass index (BMI), smoking status and HIV. In separate models, we will fit an interaction term between the treatment arm and sub-groups of interest (e.g. sex, age group, co-morbidities) to examine sub-group effect sizes and potential effect modification.

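### SAP section 7 takes visit blood pressure from readings 2 and 3 but counts the visit as missing when only reading 1 is absent, so computable values drop out of the primary analysis (minor)

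*SAP*

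**What the plan says.** SAP section 5 plans the readings: "Three measurements will be taken on the same arm in the seated position", 5 minutes apart. Protocol Aim 2, section G.b, has the same three seated readings at enrolment, 6 months and 12 months.

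SAP section 7 turns them into one value: "All analyses of blood pressure will use the average of the second and third measurement as the blood pressure measurement for that visit". The next sentence sets the missing-data rule for the primary analyses: "participants who are missing any of the three measurements will be considered to be missing blood pressure data for that visit". A sensitivity analysis follows, in which "individuals with fewer than three measurements will be included, using the average if there are two", or the single reading if there is only one.

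Three other provisions decide what the rule does:

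- Section 7 makes the primary analysis of 6-month outcomes a complete-case analysis. Protocol Aim 2, section L, likewise leaves out participants with missing 6-month data.
- Section 9.1 gives the primary model: "The response variable will be systolic blood pressure at 6 months", with arm, clinic, medication use and baseline systolic pressure as terms.
- Section 7 adds a second sensitivity analysis, in which "those with missing blood pressure data at a particular visit will be treated as having no change in blood pressure" or as uncontrolled. Sections 7 and 10 allow multiple imputation of missing outcome values.

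Neither document explains why reading 1 must be present. The protocol has no averaging rule and no requirement that all three readings exist.

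**The concern.** The two adjacent sentences in SAP section 7 do not fit together. Reading 1 never enters the visit value, yet its absence cancels that value. A participant with readings 2 and 3 has exactly the outcome that the SAP defines and is still excluded.

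The rule is written per visit, so it also covers baseline. Because baseline systolic pressure is a covariate in the primary model, an absent first reading at enrolment can remove someone whose 6-month set is complete.

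There are two side effects. First, once the visit is labelled missing, the no-change/uncontrolled analysis and the optional imputation could put an assumed or modelled value in place of an observed one. Second, the loss may be hard to see. Section 8 explains non-inclusion by withdrawal, loss to follow-up or a missed visit, and its flow chart counts attendance. Someone who attended but has an incomplete set fits none of these.

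At stake is some precision in the primary estimate, given up for no stated benefit.

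**Working it through.** **1. Which incomplete sets are excluded needlessly?**

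| Readings present | Mean of 2 and 3 computable? | Primary analysis as written | Exclusion needed by the definition? |
|---|---|---|---|
| 1, 2, 3 | yes | included | – |
| 2, 3 | yes | excluded | no |
| 1, 2 or 1, 3 | no | excluded | yes |
| one only | no | excluded | yes |

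Only the second row is inconsistent.

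**2. Reproducing the planned sample size.** Inputs from SAP section 6: difference 5 mmHg, SD 19, correlation 0.5, loss 20%, power 80%, and "an alpha of 2.5% to account for multiple testing with comparisons between the SOC and both intervention arms". The documents do not state sidedness; two-sided is assumed.

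- Residual SD after baseline adjustment: 19 × √(1 − 0.5²) = 16.45.
- Evaluable per arm: n = 2 × (2.2414 + 0.8416)² × 16.45² / 5² = 205.9, rounded up to 206.
- Enrolled per arm: 206 / 0.80 = 257.5, rounded up to 258; three arms give 774.

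This matches the SAP exactly, and the other three table rows (330, 148, 115) match by the same method. A one-sided test would give 214 per arm, and a change-score variance 344, so neither is the plan's basis.

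**3. Power if the rule removes more participants.** Let f be the share of attended visits removed by the rule beyond the 20% loss. The documents give no value for f, so the values below are assumptions. Evaluable per arm is 258 × 0.80 × (1 − f), and power is Φ[5 / (16.45 × √(2/n)) − 2.2414].

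| f (assumed) | Evaluable per arm | Power | Enrolment per arm to hold 80% |
|---|---|---|---|
| 0 | 206.4 | 80.1% | 258 |
| 1% | 204.3 | 79.7% | 261 |
| 2% | 202.3 | 79.2% | 263 |
| 5% | 196.1 | 77.9% | 272 |

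The confidence interval widens by a factor of 1/√(1 − f): 0.5% at f = 1% and 2.6% at f = 5%.

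**4. Blood pressure control.** The same visit value feeds the secondary outcome. For two proportions at the same alpha and 206.4 per arm, power is 82.0% for 30% versus 45% and 84.7% for 40% versus 56%. At f = 5% these become 79.9% and 82.7%.

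**5. What f covers.** If f is taken as all incomplete sets, the fix recovers only the part that lacks reading 1 alone, and the gain is smaller than the table shows.

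**The case against.** Several points on the other side stand.

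- **The case is narrow.** Readings are taken in sequence, so a session cut short lacks reading 3, or readings 2 and 3. Losing only reading 1 takes an unrecorded or deleted first value. Entry on tablets with field checks, and routine review for missing entries (Protocol Aim 2, sections H.a and H.e), also point to a low rate. Incomplete baseline sets should be rarer still, since blood pressure decides eligibility at enrolment.
- **The data are not lost to the trial.** A reader might infer that usable outcomes are thrown away. They are not: the sensitivity analysis for incomplete sets restores these participants, and comparing it with the primary result will show what the rule did.
- **The power figures are scenarios.** They stack assumed losses on the full 20% allowance. If follow-up beats 80%, which the home visits and tracing are meant to achieve, a loss of 1% or 2% may be absorbed.

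A further inference is that every participant with one or two readings should enter the primary analysis. The documents do not support that. Where reading 2 or 3 is absent, the SAP's value cannot be formed and exclusion follows from the definition. Admitting single readings, or means that include reading 1, would mix values of different composition in the primary endpoint; that is a trade-off, not a correction.

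What remains is that the sensitivity analysis does not repair the primary estimate. The headline result still omits participants whose defined outcome was observed.

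**Conclusion.** The inconsistency is real and minor. Participants lacking only reading 1, at baseline or at 6 months, are left out of the primary analysis without need, and two secondary procedures could replace their observed values.

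The size is unknown and probably small. Under an assumed further loss of 1% to 5% of attended visits on top of the full 20%, power is about 79.7% to 77.9% instead of 80%. This rests on the plan's own SD, correlation and difference, and on a two-sided test, which is the version that reproduces 258 per arm.

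Two stronger readings should be avoided. The planned sample size is not wrong, since it reproduces exactly. Nor do the documents show bias: nothing suggests that first readings would be absent more often in one arm. The effect shown is on precision only.

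**What to change.** In SAP section 7, change the rule for the primary analyses so that a visit is missing only if reading 2 or reading 3 is absent. Apply it at baseline and at follow-up. Under that definition the no-change/uncontrolled analysis and any imputation leave observed means of readings 2 and 3 untouched.

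Keep the existing analysis of participants with fewer than three readings as a sensitivity analysis. Do not move single readings, or two-reading means that include reading 1, into the primary outcome.

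Report the number of incomplete sets by arm and visit, showing which reading is absent, next to the section 8 flow chart.

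This is a free improvement: it needs no new data, visits or participants, leaves the outcome definition as it is, and can only keep valid observations. It should be documented before the data are examined by arm. If that point has passed, present the result under the revised rule as a labelled supplementary analysis.

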Sustainability	
 - Number of participants counseled in lifestyle modification and medication adherence at home by CBPMs. - Number of clinics adopting use and distribution of BP cuffs for HBPM. - Proportion of clinics sustaining use and distribution of BP cuffs for HBPM at 12 months, among those who distributed BP cuffs at the start of the study. - Proportion of participants retained in hypertension care at 12 months, among enrolled study participants. - Absolute change in systolic blood pressure (SBP) between 6 and 12 months after enrollment, among enrolled study participants. - Proportion of participants retained in hypertension care at 12 months, among enrolled study participants. - Absolute change in systolic blood pressure (SBP) between 6 and 12 months after enrollment, among all study participants. 	
 - CBPM study records. - Study check lists. - Study check lists. - Participant study records. - CDS records - Participant study records. - CDS records.

C. Data Sources

a. (Aim 3a) Fidelity, Sustainability, and Acceptability

Both the fidelity and the sustainability of the intervention will be assessed using data obtained through review of study check lists, the participant study records (including prescriptions), CDS records, CBPM study records, outreach team leader supervision records, and coordination meeting minutes.

Key informant and individual interviews will assess overall acceptability and experience of the intervention.

b. (Aim 3b) Cost-effectiveness

Cost data will be obtained from trial participant interviews, KZN DoH unit prices, and analysis of intervention delivery.

The trial will provide individual level outcome data on SBP and blood pressure control 6 and 12 months. The PREDICT model will use these data to predict long term effects of the interventions on quality adjusted life years (QALYs)

D. Recruitment

a. (Aim 3a) Fidelity, Sustainability, and Acceptability

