9.3 Safety measurements

The number and proportion of participants with at least one adverse event (AE), and the total number of AEs, will be tabulated by the treatment arm. AEs will be tabulated by diagnosis, severity and relationship to the intervention.

The number and proportion of participants who are still in hypertension care 6 months after enrolment will be tabulated by the treatment arm. Retention in care will be defined as currently having sufficient BP medicine in possession (taking into account the date of last visit and the amount of medication dispensed), as the primary definition. As a secondary definition, retention will be defined as having seen a health care worker for

hypertension in the past 3 months. Logistic regression will be used to estimate the OR and 95% CI for the effect of each intervention on retention in hypertension care. The model will include terms for treatment arm, clinic and active use of hypertension medication at baseline.

10. Additional exploratory analyses

The effect of each intervention (vs SOC) on mean change from baseline in systolic blood pressure over 12 months will be estimated using a linear mixed model. The response variable will be systolic blood pressure (at 6 and 12 months); the model will include fixed effects for treatment arm, visit, a treatment arm-visit interaction term, randomisation strata (clinic and active use of hypertension medication at enrolment) and baseline systolic blood pressure, and participant as a random effect to account for correlation of repeated measurements within the participant. The inclusion of the interaction term allows the effect of the intervention to differ over time. If the interaction term is not statistically significant at $p < 0.10$, we will drop it from the model and estimate the overall effect of each intervention (vs SOC) on the change in systolic blood pressure during the trial.

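### Six-month retention in care falls under the SAP's complete-case rule with no analysis for missing status, so retention is likely to be overstated

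*SAP*

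**What the plan says.** The SAP (section 2) and the protocol (Aim 2, section K) both list 6-month retention as a safety measure: "Proportion of participations retained in hypertension care at 6 months". Neither states a denominator.

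SAP section 9.3 plans a tabulation and a logistic model: "The number and proportion of participants who are still in hypertension care 6 months after enrolment will be tabulated by the treatment arm". The primary definition is "Retention in care will be defined as currently having sufficient BP medicine in possession", determined by "taking into account the date of last visit and the amount of medication dispensed". The secondary definition is contact with a health care worker about hypertension in the past 3 months. The section does not say where these data come from or what happens when status is unknown.

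SAP section 7 makes two statements about who is analysed. The general one is "All analyses will be conducted using the intention-to-treat principle, where all randomised participants will be included in the analysis", irrespective of adherence. The narrower one sets complete case as primary for outcomes from the 6-month visit: "the primary analyses will be restricted to participants with the relevant outcome data at 6 months (complete case".

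The section 7 sensitivity analysis for missing data sets blood pressure to unchanged or uncontrolled. The multiple imputation that section 10 allows is also for blood pressure. Neither mentions retention.

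For 12 months, protocol Table 4 does name a population: "Proportion of participants retained in hypertension care at 12 months, among enrolled study participants".

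**The concern.** For most outcomes, complete case is a choice about missing data. For retention it comes close to selecting on the outcome, because a person who has moved away, withdrawn or stopped engaging is both harder to find at 6 months and less likely to hold medicine or have seen a health worker. Dropping such people raises the retained proportion.

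The measure matters here. The protocol's risk section for Aim 2 recognises that participants in the two community arms could receive less than standard care because they do not attend the clinic. Of the listed safety measures, retention is the closest to that risk. The plan gives blood pressure control a missing-as-failure check but gives none to retention, where missingness is more plausibly tied to the result.

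**Working it through.** **1. The planned amount of missing data.** Inputs from SAP section 6: difference 5 mmHg, SD 19 mmHg, correlation 0.5, two-sided alpha 0.025, power 80%, loss 20%.

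- SD after adjustment for baseline = 19 × √(1 − 0.5²) = 16.45 mmHg.
- n per arm = 2 × (2.241 + 0.842)² × 16.45² / 5² ≈ 206.
- Enrolled per arm = 206 / 0.8 = 257.5, rounded up to 258; three arms give 774.

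The stated sample size is reproduced. The plan therefore allows for 0.20 × 258 = 51.6 participants per arm without 6-month data (0.20 × 774 = 154.8 in all).

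**2. Error in the retained proportion.** Let d be the loss, r the retention among those observed and q the retention among those missing.

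- Retention in all randomised = (1 − d) × r + d × q.
- Complete-case error = r − that value = d × (r − q).

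The documents give no retention rate, so r = 85% and all values of q are assumptions. With d = 20%:

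| q | Retention in all randomised | Complete-case error (points) |
|---|---|---|
| 100% | 0.68 + 0.20 = 88% | −3 (understated) |
| 85% | 0.68 + 0.17 = 85% | 0 |
| 50% | 0.68 + 0.10 = 78% | +7 |
| 30% | 0.68 + 0.06 = 74% | +11 |
| 0% | 0.68 + 0 = 68% | +17 |

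The upper limit is d × r. At 20% loss it is 12, 14, 16 and 18 points for r = 60%, 70%, 80% and 90%. With r = 85% it is 0.10 × 85 = 8.5 points at 10% loss and 0.05 × 85 = 4.25 points at 5% loss.

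**3. Error in the comparison between arms.** If d, r and q are the same in both arms, the true and complete-case differences are both zero. Now suppose r = 85% in both arms, with loss of 25% in SOC and 15% in an intervention arm (assumed):

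- q = 30%: SOC 0.75 × 0.85 + 0.25 × 0.30 = 71.25%; intervention 0.85 × 0.85 + 0.15 × 0.30 = 76.75%; difference 5.5 points.
- q = 50%: SOC 76.25%; intervention 79.75%; difference 3.5 points.

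Complete case reports a difference of 0 and an odds ratio of 1.00 in both cases. Counting every unknown as not retained (q = 0) gives SOC 0.75 × 0.85 = 63.75% and intervention 0.85 × 0.85 = 72.25%. The odds ratio is then (0.7225/0.2775) / (0.6375/0.3625) = 1.48. If the two losses are exchanged, every sign reverses and the odds ratio is 1/1.48 = 0.68. That second pattern is the one in which complete case would hide poorer retention in a community arm.

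**The case against.** A reader might infer that the SAP analyses retention only in people who attended the 6-month visit and that the reported figure is therefore inflated. The documents do not go that far, for these reasons.

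- **The restriction is to people with the relevant outcome data.** Date of last visit and amount dispensed could be taken from records, so a non-attender could still be classified. This stands. However, section 9.3 names no such source, and whoever remains unclassified is still dropped.
- **A missed research visit is not departure from care.** The Aim 2 overview places outcome visits outside clinical care. Missed visits lead to calls and tracing in the protocol, and SAP section 5 adds an attempted home visit. This stands: it may bring loss below 20% and raise q, and it makes overstatement likely but not certain.
- **Most of the magnitude is assumed.** Only the 20% loss comes from the plan. Protocol section L expects no differential loss, and with equal loss and equal rates the comparison is unaffected. This stands, but an expectation does not replace a planned check in a trial whose participants and clinic staff know the allocation.
- **Loss would be visible.** SAP section 8 shows attendance and withdrawals by arm and compares included with excluded participants. This helps a careful reader, but the retention estimate and its odds ratio would still rest on the reduced set.
- **The 12-month measure belongs to Aim 3.** The SAP leaves that aim to a separate plan, and naming enrolled participants as the population does not say how unknown status is handled. The two denominators need reconciling; an outright contradiction is not shown.

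**Conclusion.** The point holds as a gap with a likely direction of bias. Read together, sections 7 and 9.3 would analyse 6-month retention only in those whose status is known, and nothing in the plan tests that choice. At the planned 20% loss and an assumed 85% observed retention, the overstatement is 0 if the missing are retained equally often, 7 to 11 points if 30% to 50% of them are in care, and 17 points at most. It turns into a small understatement, up to 3 points, only if the missing are retained more often than those observed. The comparison between arms can move either way, and only if loss or the retention gap between observed and missing participants differs by arm. The documents do not establish that retention will be overstated, or that a harm will be hidden. Retention is a safety measure without a power calculation, so the sample size is unaffected.

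**What to change.** Amend SAP section 9.3 to:

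1. Report 6-month retention with all randomised participants as the denominator, and reconcile this with the two section 7 statements and with the 12-month measure in protocol Table 4.
2. Name the data source. For participants without a 6-month visit, use date of last visit and dispensing data where these are available from the same source in all three arms.
3. Add an analysis that counts unknown status as not retained, mirroring the blood pressure rule. Show deaths separately and give the number with unknown status by arm.
4. Report this beside the complete-case result.

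The wording and the extra model cost almost nothing. Step 2 may need more work: the protocol text places clinic record review at enrolment and, for SOC, at 12 months, and the 6-month record review belongs to the costing study. A 6-month dispensing check on everyone without a visit is therefore not clearly planned already.

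There are two downsides. Reported retention may look lower. Counting unknowns as not retained will also misclassify some people still in care, possibly more in SOC, since the community arms generate home-visit and decision-support records that SOC does not. For that reason the two results should be read together, with the number unknown in each arm in view.
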